## **4. STUDY DESIGN AND RATIONALE**

### **4.1. Description of Study Design**

This study is a single arm, non-randomized, open label, bilateral, non-dispensing clinical trial. There is one study visit. Each subject will wear lenses for approximately 30-90 minutes. The key assessments for this study will be the number of fitting modifications and ECP feedback throughout the fit process while using the Fit Guide. Each ECP will fit a maximum of 4 subjects a. At the conclusion of the study subjects will not have access to the investigational lenses. The marketed Moist Multifocal lenses can be obtained from their own

[REDACTED] (5)

ECP, at the subjects discretion, however no marketed product or contact lens prescriptions will be given to the subject to use outside of this clinical trial.

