1.13	Add Refinement	Place the BCC result in the trial frame and refine the near prescription with trial lenses (or flippers) under binocular conditions.	
1.14	Near Visual Acuity	Using the ETDRS 2000 Series Chart 1 or 2 near card placed at 40 cm. Record the near visual acuity OD, OS and OU at 40 cm.	
1.15	Biomicroscopy	
FDA Slit Lamp Classification Scale will be used to grade the findings and determine eligibility.
 
For the conjunctival redness [REDACTED] 0.5 unit increments will be used in the grading. Corneal Staining Assessment [REDACTED] will be graded in 1.0 increments.
 
If any of these slit lamp findings are Grade 3 or higher, the subject will be discontinued. If discontinued a final examination must be completed.
 
If the clearance of the fluorescein needs to be expedited, preservative-free rewetting drops or saline may be instilled.
	
1.16	Eligibility after Baseline	All responses to Inclusion Criteria questions must be answered "yes" and all responses to Exclusion Criteria questions must be answered "no" for the subject to be considered eligible.	

Visit 1: Treatment 1 Lens Fitting			
Step	Procedure	Details	
1.17	ECP Global ID	ADD the ECP's global ID.	
1.18	ECP Lens Selection	The ECP will be provided with the fitting guide and determine the initial study lens selection. The study staff will select the lens pair and power for each eye. Record the test	Appendix F/G Fitting Guides

		lens parameters (power and lot number).	
1.19	Lens insertion	
Subjects will insert the lenses themselves. If the lens is uncomfortable, inspect for damage and remove, reinsert or replace as necessary. Damaged lenses will be stored in labeled vial with sterile saline, and clearly differentiated from the other worn lenses that will be shipped back to the Sponsor. Complete the Quality Product Complaint form.
	
1.20	Toric Fit Evaluation (if applicable)	
The principal or Co-Investigator will evaluate the toric fit and record:
 
 
• The rotational position to the nearest degree
 
• Lens stability with blink
 
• Lens stability with eye versions
 
• Toric fit acceptable or unacceptable
 
 
Toric lens fit will be unacceptable if lenses rotated more than 40 degrees, or lens stability is worse than 5 degrees movement with blink. If toric fit is unacceptable, remove the lenses, perform biomicroscopy and proceed to final evaluation.
	

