1.21	Lens Fit Assessment	
The principal or Co-Investigator will evaluate the general lens fit. Lens fit will be assessed in primary gaze, upgaze & Josephson push up test.
 
An unacceptable lens fit will be any one or more of the following:
 
 
• presence of limbal exposure (appearance of clear cornea) in any gaze
 
• presence of edge lift
 
• Presence of unacceptable movement (excessive or insufficient) in all three movement categories (primary gaze, upgaze, and push-up).
 
 
If either lens is deemed unacceptable, the subject will be discontinued from the study. Perform a slit-lamp evaluation and complete the Final Evaluation
	

████████ (5)

1.22	Lens Settling	Allow the study lenses to continue to settle for a minimum of 15 minutes from the time of lens insertion	
1.23	ECP Fitting with Fit Guide	The ECP will be provided the fitting guides and assess the vision provided by the lenses and will determine if a lens change is needed. The fitting activities of the ECP will be videotaped. During the fitting of the lenses the ECP may use the slit lamp to evaluate the fit of the lens. .	Appendix F/G Fitting Guides
1.24	Modifications (if necessary)	If the ECP determines a change in lenses is required they will be allowed two Modifications. If modification is needed complete steps 1.18 to 1.19 for each lens change.	Appendix F/G Fitting Guides
1.25	Post-Fit Questionnaire	The subject will evaluate the vision characteristics, comfort characteristics, handling characteristics, and visual symptoms of the study lenses using the PRO questionnaire. Subjects will also be shown a product concept of the lens they have just worn and their feedback regarding the concept will be collected.	Appendix A and H
1.26	Exit Biomicroscopy	The Principal Investigator or Co-Investigator will perform biomicroscopy OD and OS. Slit Lamp Classification Scales will be used to grade the findings. For the conjunctival redness [REDACTED] 0.5 unit increments will be used in the grading. Corneal Staining Assessment [REDACTED] will be graded in 1.0 increments.	[REDACTED]
1.27	ECP Interview	The ECP will be interviewed regarding their experience fitting the subject using the Fit Guide.	Appendix I

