### **8.2. Withdrawal/Discontinuation from the Study**

A subject will be withdrawn from the study for any of the following reasons:

- Subject death during the study period
- Subject withdrawal of consent
- Subject not compliant to protocol
- Subject lost to follow-up
- Subject no longer meets eligibility criteria (e.g. the subject becomes pregnant)
- Subject develops significant or serious adverse events causing discontinuation of study lens wear
- Subjects who have experienced a Corneal infiltrative Event (CIE)
- Investigator's clinical judgment regarding the subject safety reasons (that it is in the best interest of the subject to stop treatment)
- Subject not compliant with study lens wear schedule
- Subject not successfully dispensed due to lack of efficacy and safety including poor vision, poor comfort or unacceptable fit

For discontinued subjects, the Investigator will:

- Complete the current visit (scheduled or unscheduled)
- Complete the Final Evaluation, indicating the reason that the subject was discontinued from the study
- Record the spherocylindrical refraction with best corrected distance visual acuity
- Collect used Test article(s) (worn or brought to the visit) from the subject and discard them, unless otherwise stated in Section 7.2
- Collect all unused Test article(s) from the subject

An additional subject may be enrolled if a subject discontinues from the study prematurely.

In cases where a subject is lost to follow-up, every possible effort must be made to contact the subject and determine the reason for discontinuation/withdrawal. The measures taken to follow up must be documented including two written attempts and a certified letter (or equivalent) as the final attempt.

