## 14. STATISTICAL METHODS

### 14.1. General Considerations

All data summaries and statistical analyses will be performed using the SAS software Version 9.4 (SAS Institute, Cary, NC). Throughout the analysis of data, the results for each subject/eye will be used when available for summarization and statistical analysis. Unscheduled visits will be summarized separately and will be excluded from the statistical analysis.

Summary tables (Descriptive statistics and/or frequency tables) will be provided for all baseline variables, efficacy variables and safety variables as appropriate. Continuous variables will be summarized with descriptive statistics (n, mean, standard deviation (SD), median, minimum and maximum). Frequency count and percentage of subjects or eyes within each category will be provided for categorical data.

Summaries will be presented by study lens type and will be performed separately by completion status. All analyses will be conducted on per-protocol population (see section 14.3).

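### Sections 7.2 and 8.2 disagree on whether the ECP interview and subject survey follow an unacceptable fit, so feedback on failed fits may be missing or unevenly collected

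*Combined protocol and SAP*

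**What the plan says.** Section 7.2 gives two early exits once the first pair is on the eye.

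- Step 1.20, toric fit: "If toric fit is unacceptable, remove the lenses, perform biomicroscopy and proceed to final evaluation".
- Step 1.21, general fit: "If either lens is deemed unacceptable, the subject will be discontinued from the study", followed by "Perform a slit-lamp evaluation and complete the Final Evaluation".

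The subject survey (step 1.25) and the ECP interview (step 1.27) come later in the same table. The interview is tied to the individual subject: "The ECP will be interviewed regarding their experience fitting the subject using the Fit Guide". The Final Evaluation has two items, a refraction (F.1) and the final exam form (F.2).

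Section 8.2 lists among its withdrawal reasons "Subject not successfully dispensed due to lack of efficacy and safety including poor vision, poor comfort or unacceptable fit". Its first action for discontinued subjects is "Complete the current visit (scheduled or unscheduled", and completing the Final Evaluation is a separate item. Section 4.1 says "There is one study visit".

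Table 3 lists the ECP interview as its last row, after the Final Evaluation. On reporting, Section 14.1 says: "Summaries will be presented by study lens type and will be performed separately by completion status".

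**The concern.** All three secondary endpoints in Section 2.2 (ECP feedback on the process, ECP feedback on the layout, and the subject survey) depend on steps 1.25 and 1.27. Section 4.2 names ECP feedback on fitting as the study's primary aim. The ECP has already used the guide to choose the first pair at step 1.18, before either exit can occur.

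A site working down the step table would finish a failed fit without the survey or the interview. A site working from 8.2 would collect both. Under the first practice, whether feedback exists depends on the outcome of the fit. The first secondary endpoint asks for weaknesses of the guide as well as strengths, and an unsuccessful fitting is a natural place to hear about weaknesses. Section 8.2 also lets an additional subject be enrolled after a discontinuation, so a case without feedback may be replaced by one with it.

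**Working it through.** The plan gives no figure for failed fits, so there is none to reproduce. The sample-size table in 14.2 concerns the primary endpoint and does not enter here. The check is a reading of the passages together, followed by a scale calculation.

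**1. What a stopped subject still receives under 7.2.** After step 1.20 or 1.21 the subject has a biomicroscopy or slit-lamp examination, in effect the procedure of step 1.26, and then F.1 and F.2. Settling (1.22), the ECP's vision assessment (1.23), modifications (1.24), the survey (1.25) and the interview (1.27) are not mentioned. Step 1.24 repeats only steps 1.18 and 1.19 for a lens change, so as written the exits apply to the first pair.

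**2. What the same subject should receive under 8.2.** Unacceptable fit is a listed withdrawal reason, so the actions for discontinued subjects apply. The current visit and the Final Evaluation are both to be completed. With one visit, the current visit is Visit 1, which contains 1.25 and 1.27.

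**3. Whether any text settles the conflict.** Section 8.2 defers to 7.2 only on the handling of used lenses. Table 3 and 7.2 put the interview on opposite sides of the Final Evaluation, so the order of procedures does not settle it either.

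**4. Scale.** Inputs: about 32 enrolled and 24 targeted to complete (Section 4.3), which leaves 32 − 24 = 8 non-completers for all reasons, or 8/32 = 25%. Let k be the number stopped at 1.20 or 1.21. This is an assumption, since the documents give no rate. The share of fitted subjects without survey and interview under a literal reading of 7.2 is k/(24 + k):

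| k (assumed) | Following 7.2 literally | Following 8.2 |
|---|---|---|
| 1 | 1/25 = 4% | 0% |
| 2 | 2/26 = 7.7% | 0% |
| 4 | 4/28 = 14.3% | 0% |
| 6 | 6/30 = 20% | 0% |
| 8 | 8/32 = 25% | 0% |

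The last row is a ceiling, because it treats every non-completer as a failed fit.

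**5. Per ECP.** The Synopsis has each ECP fit 3 or 4 subjects. One stopped subject is therefore 1/4 = 25% to 1/3 = 33% of that ECP's cases.

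**6. Whether collected answers would be reported.** Section 14.1 places all analyses on the per-protocol population, which 14.3 limits to subjects who completed all visits. Section 14.6 plans no secondary analysis. The only place for answers from stopped subjects is the summary by completion status in 14.1.

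**The case against.** The strongest reply is that this is a wording mismatch with little riding on it. Several parts of that reply stand.

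- *Loss is not certain.* A reader of 7.2 alone might infer that the feedback is lost for every failed fit. The documents do not support that. Section 8.2 would have it collected, and Table 3 allows the interview after the Final Evaluation. The interview needs the ECP rather than the subject, and the same ECP would ordinarily be interviewed about other subjects. The survey is the more exposed of the two.
- *These are not plainly failures of the guide.* A reader might count each stopped subject as an unfavourable verdict on it. The exit criteria are physical (rotation, stability, limbal exposure, edge lift, movement) and are judged by the principal or co-investigator. Table 1 gives each lens one base curve and one diameter, so the ECP has no other geometry to choose. Subjects whose vision remains poor after two modifications have passed these exits and can still reach 1.25 and 1.27.
- *Survey answers after brief wear are of limited meaning.* Both exits precede the settling step and the vision assessment. Items on visual performance or price would not be comparable with completers' answers. Items on satisfaction with the fitting process, and on what the subject would improve about it, would still make sense.
- *Such fits may be few.* Section 14.5 itself refers to potentially low rates of unacceptable fitting.
- *No test depends on it.* There are no secondary hypotheses and no secondary analysis.

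The fitting guides and interview materials are redacted, so it cannot be seen whether the interview is designed to cover a stopped fit. What remains is that two sections instruct the site differently on data central to the stated aim, and that the difference applies only when the fit fails.

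**Conclusion.** The contradiction is real and the passages need to be reconciled. As written, ECP feedback and the subject survey may be missing or inconsistently collected for failed fits, selectively by fit outcome. The likely direction is favourable to the guide, but that is a judgement and not something the documents show.

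The affected share is 0% if sites follow 8.2. It is 4% to 25% of fitted subjects if they follow 7.2 literally and 1 to 8 failures are assumed alongside 24 completers. A reader might go further and state by how many percentage points satisfaction would be overstated. That needs satisfaction rates for completers and for stopped subjects, and the documents give neither, so no such figure is supported.

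This is a worthwhile, inexpensive correction. It does not threaten the primary conclusion: the primary endpoint and the 14.2 power table are unaffected by it.

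**What to change.** Reconcile 7.2, 8.2 and Table 3 on data collection after an unacceptable fit:

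- In steps 1.20 and 1.21, after the examination already required, state that the ECP interview (1.27) is still done, together with those items of step 1.25 that apply to the wear obtained, such as satisfaction with the fitting process and the one thing to improve. List those items in advance.
- Give the interview the same position in Table 3 and 7.2, and have 8.2 refer to the wording in 7.2.
- Report these answers descriptively in the non-completer summary that 14.1 already calls for. State that this summary is not restricted to the per-protocol population, and do not pool the answers with those of completers.

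The clinical handling of the unacceptable fit stays as written.

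The cost is a few sentences of text plus, for each stopped subject, one short interview and a partial questionnaire. The instruments are already in the protocol. The downside is that survey answers after brief wear are harder to interpret, which is why they should be shown separately.

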## **FINAL EVALUATION**

The final evaluation will ordinarily take place immediately following the last scheduled follow-up visit per the study protocol. It may also take place at any point the subject discontinues the study or is terminated from the study.

Final Evaluation			
Step	Procedure	Details	
F.1	Subjective spherocylindrical Refraction	Complete optimal binocular balanced spherocylindrical refraction and record the resultant distance visual acuity (OD, OS and OU) to the nearest letter.	
F.2	Final Exam Form	Indicate if the subject completed the study successfully. If subject discontinued from the study indicate the reason.	

### **7.3. Unscheduled Visits**

If, during the investigation, a subject requires an unscheduled visit to the clinical site, the following information will be collected at a minimum:

- Chief complaint prompting the visit. If the reason is an adverse event, the applicable eCRF for the adverse event must be completed and subject record completed as appropriate
- Date and time of the visit and all procedures completed at the unscheduled visit
- Review of adverse event and concomitant medications
- Documentation of any Test article dispensed or collected from the subject, if applicable
- Slit lamp findings (using the Slit Lamp Classification Scale)

If the Investigator withdraws a subject from the study, the final study visit case report forms must be completed indicating the reason(s) why the subject was withdrawn. The subject record must be completed documenting the date and primary reason for withdrawal and the study CRA notified.

Any ocular and non-ocular Adverse Events that are ongoing at the time of the study visit will be followed by the Investigator, within licensure, until they have resolved, returned to pre-treatment status, stabilized, or been satisfactorily explained. If further treatment i.e., beyond licensure is required, the subject will be referred to the appropriate health care provider.

(5)

The following information will be collected during an unscheduled visit.

Step	Procedure	Details	
U.1	Chief Complaints	Record the subject's chief complaints for reasons for the unscheduled visit	
U.2	Change of Medical History and Concomitant Medications	Questions regarding the change of subjects' medical history and concomitant medications.	
U.3	Entrance VA	Record the entrance distance visual acuity (OD, OS and OU) to the nearest letter.	
U.4	Subjective Sphero-cylindrical Refraction	Perform bare-eye subjective sphero-cylindrical refraction with a phoropter (adopt the maximum plus to maximum visual acuity (MPMVA) approach and use the duo-chrome test for binocular balancing) and record the best corrected distance visual acuity to the nearest letter (OD, OS, OU).	
U.5	Slit Lamp Biomicroscopy	FDA Slit Lamp Classification Scale will be used to grade the findings. If no slit lamp finding is noted on the EDC form it is considered as a zero "0" Grade for all observations listed. After the slit lamp examination, at the discretion of the Investigator, rinse the subject's eyes thoroughly with preservative-free saline.	
U.6	Exit Visual Acuity	Record the subject's exit distance visual acuity (OD, OS and OU) to the nearest letter with the subjects wearing the study provided spectacle glasses.	

#### 7.4. Laboratory Procedures

Not Applicable

### 8. SUBJECTS COMPLETION/WITHDRAWAL

#### 8.1. Completion Criteria

Subjects are considered to have completed the study if they:

- provided informed consent;
- they are eligible;

(5)

- have not withdrawn/discontinued for any reason described in Section 8.2;
- Complete all study visits

### **8.2. Withdrawal/Discontinuation from the Study**

A subject will be withdrawn from the study for any of the following reasons:

- Subject death during the study period
- Subject withdrawal of consent
- Subject not compliant to protocol
- Subject lost to follow-up
- Subject no longer meets eligibility criteria (e.g. the subject becomes pregnant)
- Subject develops significant or serious adverse events causing discontinuation of study lens wear
- Subjects who have experienced a Corneal infiltrative Event (CIE)
- Investigator's clinical judgment regarding the subject safety reasons (that it is in the best interest of the subject to stop treatment)
- Subject not compliant with study lens wear schedule
- Subject not successfully dispensed due to lack of efficacy and safety including poor vision, poor comfort or unacceptable fit

For discontinued subjects, the Investigator will:

- Complete the current visit (scheduled or unscheduled)
- Complete the Final Evaluation, indicating the reason that the subject was discontinued from the study
- Record the spherocylindrical refraction with best corrected distance visual acuity
- Collect used Test article(s) (worn or brought to the visit) from the subject and discard them, unless otherwise stated in Section 7.2
- Collect all unused Test article(s) from the subject

An additional subject may be enrolled if a subject discontinues from the study prematurely.

In cases where a subject is lost to follow-up, every possible effort must be made to contact the subject and determine the reason for discontinuation/withdrawal. The measures taken to follow up must be documented including two written attempts and a certified letter (or equivalent) as the final attempt.

## **9. PRE-STUDY AND CONCOMITANT INTERVENTION/MEDICATION**

Concomitant medications will be documented during screening and updated during the study. Disallowed medications for this study include: Any ocular medications with the exception of rewetting drops.

[REDACTED] (5)

Concomitant therapies that are disallowed include: Any therapies that may contraindicate lens wear.

## **10. DEVIATIONS FROM THE PROTOCOL**

Investigator will notify study sponsor upon identification of a protocol deviation. Major protocol deviations must be reported to the sponsor within 24 hours after discovery of the protocol deviation. The Investigator will report deviations per IRB/IEC requirements. All deviations will be tracked and corrective actions implemented as appropriate.

If it becomes necessary for the Investigator to implement a deviation in order to eliminate an immediate hazard to the trial subject, the Investigator may implement the deviation immediately without notification to the sponsor. Within 24 hours after the implemented deviation, the Investigator must notify and provide the rationale to the Sponsor and, as required, the IEC/IRB.

## **11. STUDY TERMINATION**

If more than 2 subjects in the investigational soft contact lens group develop serious expected (e.g., definite or probable MK) or unexpected device related adverse events, the study will be suspended. Upon review and consultation with IRB, and JJVC safety review committee, the study may be terminated.

The occurrence of one or more Unanticipated Serious Adverse Device Effect (USADE), or any SAE where the relationship to study agent cannot be ruled out, may result in stopping further dispensing of Test article. In the event of a USADE or SAE, the Sponsor may unmask the treatment regimen for the subject(s) and will discuss this with the Investigator before any further subjects are enrolled.

The Sponsor will determine when a study will be stopped. The Principal Investigator always has the discretion to initiate stopping the study based on patient safety or if information indicates the study's results are compromised.

JJVC reserves the right to terminate the study at any time for any reason. Additionally, the IEC/IRB reserves the right to terminate the study if an unreasonable risk is determined. The study can be terminated by the Principal Investigator at the individual clinical site due to specific clinical observations, if in their opinion, after a discussion with JJVC, it is determined that it would be unwise to continue at the clinical site.

JJVC (and the IEC/IRB and DMC, if applicable) will evaluate all adverse events. If it is determined that an adverse event presents an unreasonable risk, the investigation, or that part of the investigation presenting the risk, will be terminated, as soon as possible.

[REDACTED] (5)

Should the study be terminated (either prematurely or as scheduled), the Investigator will notify the IEC/IRB and Regulatory Authority as required by local regulatory requirements.

